5.2.1.4 Mid-Cycle Labs for Patients on Doxorubicin

As is our standard practice, all patients receiving doxorubicin will have a CBC and CMP drawn 10-14 days after their infusion. If these labs are drawn at an outside lab they must be faxed to the Seattle Cancer Care Alliance and reviewed by a nurse and the study team. A nurse will call the patient to inquire about any unexpected subjective toxicity. The patient's physician will be made aware of any unexpected toxicity and any critical lab values.

5.2.2 Timing of Dose Administration

Trial treatment should be administered on Day 1 of each 21-day cycle after all procedures/assessments have been completed as detailed on the Trial Flow Chart (Section 6.0). Trial treatment may be administered up to 3 days before or after the scheduled Day 1 of each cycle due to administrative reasons.

All trial treatments will be administered on an outpatient basis.

Pembrolizumab will be administered as a 30 minute IV infusion every 3 weeks. Sites should make every effort to target infusion timing to be as close to 30 minutes as possible.

However, given the variability of infusion pumps from site to site, a window of -5 minutes and +10 minutes is permitted (i.e., infusion time is 30 minutes: -5 min/+10 min).

The Pharmacy Manual contains specific instructions for the preparation of the pembrolizumab infusion fluid and administration of infusion solution.

Doxorubicin is typically given over a 1-hour infusion but this could be stretched to 3 hours for relief of acute symptoms such as nausea.

5.2.3 Trial Blinding/Masking

This is an open-label trial; therefore, the investigator and subject will know the treatment administered.

5.3 Concomitant Medications/Vaccinations (allowed & prohibited)

Medications or vaccinations specifically prohibited in the exclusion criteria are not allowed during the ongoing trial. If there is a clinical indication for one of these or other medications or vaccinations specifically prohibited during the trial, discontinuation from trial therapy or vaccination may be required. The investigator should discuss any questions regarding this with the Merck Clinical team. The final decision on any supportive therapy or vaccination rests with the investigator and/or the subject's primary physician.

5.3.1 Acceptable Concomitant Medications

All treatments that the investigator considers necessary for a subject's welfare may be administered at the discretion of the investigator in keeping with the community standards of medical care. All concomitant medication will be recorded on the case report form (CRF) including all prescription, over-the-counter (OTC), herbal supplements, and IV medications and fluids. If changes occur during the trial period, documentation of drug dosage, frequency, route, and date may also be included on the CRF.

All concomitant medications received within 28 days before the first dose of trial treatment and 30 days after the last dose of trial treatment should be recorded. Concomitant medications administered after 30 days after the last dose of trial treatment should be recorded for SAEs and ECIs as defined in Section 7.2.

5.3.2 Prohibited Concomitant Medications

Subjects are prohibited from receiving the following therapies during the Screening and Treatment Phase (including retreatment for post-complete response relapse) of this trial:

- Antineoplastic systemic chemotherapy or biological therapy
- Immunotherapy not specified in this protocol
- Chemotherapy not specified in this protocol
- Investigational agents other than pembrolizumab

- Radiation therapy
 - Note: Radiation therapy to a symptomatic solitary lesion or to the brain may be allowed at the investigator's discretion. Because doxorubicin increases radiation related toxicity, the patient must have completed doxorubicin and be on the Pembrolizumab alone portion of the treatment to undergo radiation. Radiation must begin at least 1 week after the last pembrolizumab dose and complete 1 week prior to the following dose. Dose delays of up to 3 weeks are acceptable in order to achieve this.
 - If the radiation is necessary as a result of progression, the patients should be treated as if they had progressed (e.g. they can continue pembrolizumab and have a confirmatory scan done after 2 cycles).
- Live vaccines within 30 days prior to the first dose of trial treatment and while participating in the trial. Examples of live vaccines include, but are not limited to, the following: measles, mumps, rubella, varicella/zoster, yellow fever, rabies, BCG, and typhoid vaccine.
- Systemic glucocorticoids for any purpose other than to modulate symptoms from an event of clinical interest of suspected immunologic etiology or for refractory doxorubicin-related nausea and vomiting. The use of physiologic doses of corticosteroids may be approved after consultation with the principal investigator and Merck.

Subjects who, in the assessment by the investigator, require the use of any of the aforementioned treatments for clinical management should be removed from the trial. Subjects may receive other medications that the investigator deems to be medically necessary.

The Exclusion Criteria describes other medications which are prohibited in this trial.

There are no prohibited therapies during the Post-Treatment Follow-up Phase.

5.4 Rescue Medications & Supportive Care

5.4.1 Supportive Care Guideline

Subjects should receive appropriate supportive care measures as deemed necessary by the treating investigator. Suggested supportive care measures for the management of adverse events with potential immunologic etiology are outlined along with the dose modification guidelines in Section 5.2.1.2, [Table 3]. Where appropriate, these guidelines include the use of oral or intravenous treatment with corticosteroids as well as additional anti-inflammatory agents if symptoms do not improve with administration of corticosteroids. Note that several courses of steroid tapering may be necessary as symptoms may worsen when the steroid dose is decreased. For each disorder, attempts should be made to rule out other causes such as metastatic disease or bacterial or viral infection, which might require additional supportive

care. The treatment guidelines are intended to be applied when the investigator determines the events to be related to pembrolizumab.

Note: if after the evaluation the event is determined not to be related to pembrolizumab, the investigator does not need to follow the treatment guidance. Refer to Table 3 in Section 5.2.1.2 for dose modification guidelines and supportive care.

It may be necessary to perform conditional procedures such as bronchoscopy, endoscopy, or skin photography as part of evaluation of the event.

While not an absolute protocol requirement, investigators are highly encouraged to use a cardioprotective agent such as dexrazoxane beginning at cycle 5 to doxorubicin. This will help to lower the cardiac risk if the patient progresses and chooses to receive additional doxorubicin along with olaratumab in a subsequent line of therapy.

5.5 Diet/Activity/Other Considerations

5.5.1 Diet

Subjects should maintain a normal diet unless modifications are required to manage an AE such as diarrhea, nausea or vomiting.

5.5.2 Contraception

Pembrolizumab may have adverse effects on a fetus in utero. Furthermore, it is not known if pembrolizumab has transient adverse effects on the composition of sperm. Non-pregnant, non-breast-feeding women may be enrolled if they are willing to use 2 methods of birth control or are considered highly unlikely to conceive. Highly unlikely to conceive is defined as 1) surgically sterilized, or 2) postmenopausal (a woman who is ≥ 5 years of age and has not had menses for greater than 1 year will be considered postmenopausal), or 3) not heterosexually active for the duration of the study. The two birth control methods can be either two barrier methods or a barrier method plus a hormonal method to prevent pregnancy. Subjects should start using birth control from study Visit 1 throughout the study period up to 120 days after the last dose of study therapy.

The following are considered adequate barrier methods of contraception: diaphragm, condom (by the partner), copper intrauterine device, sponge, or spermicide. Appropriate hormonal contraceptives will include any registered and marketed contraceptive agent that contains an estrogen and/or a progestational agent (including oral, subcutaneous, intrauterine, or intramuscular agents).

Subjects should be informed that taking the study medication may involve unknown risks to the fetus (unborn baby) if pregnancy were to occur during the study. In order to participate in the study they must adhere to the contraception requirement (described above) for the duration of the study and during the follow-up period defined in section 7.2.2-Reporting of Pregnancy and Lactation to the Sponsor-Investigator and to Merck. If there is any question

that a subject will not reliably comply with the requirements for contraception, that subject should not be entered into the study.

5.5.3 Use in Pregnancy

If a subject inadvertently becomes pregnant while on treatment with pembrolizumab, the subject will immediately be removed from the study. The site will contact the subject at least monthly and document the subject's status until the pregnancy has been completed or terminated. The outcome of the pregnancy will be reported to the Sponsor-Investigator and to Merck without delay and within 24 hours to the Sponsor-Investigator and within 2 working days to Merck if the outcome is a serious adverse experience (e.g., death, abortion, congenital anomaly, or other disabling or life-threatening complication to the mother or newborn).

The study investigator will make every effort to obtain permission to follow the outcome of the pregnancy and report the condition of the fetus or newborn to the Sponsor-Investigator. If a male subject impregnates his female partner the study personnel at the site must be informed immediately and the pregnancy reported to the Sponsor-Investigator and to Merck and followed as described above and in Section 7.2.2.

5.5.4 Use in Nursing Women

It is unknown whether pembrolizumab is excreted in human milk. Since many drugs are excreted in human milk, and because of the potential for serious adverse reactions in the nursing infant, subjects who are breast-feeding are not eligible for enrollment.

5.6 Subject Withdrawal/Discontinuation Criteria

Subjects may withdraw consent at any time for any reason or be dropped from the trial at the discretion of the investigator should any untoward effect occur. In addition, a subject may be withdrawn by the investigator or the Sponsor-Investigator if enrollment into the trial is inappropriate, the trial plan is violated, or for administrative and/or other safety reasons. A subject will be considered withdrawn and no longer followed if they enroll onto hospice care. Specific details regarding discontinuation or withdrawal are provided in Section 7.1.4 – Other Procedures.

A subject must be discontinued from the trial for any of the following reasons:

- The subject or legal representative (such as a parent or legal guardian) withdraws consent.
- Confirmed radiographic disease progression

Note: For unconfirmed radiographic disease progression, please see Section 5.2.2

- Unacceptable adverse experiences as described in Section 5.2.1.2

- Intercurrent illness that prevents further administration of treatment
- Investigator's decision to withdraw the subject
- The subject has a confirmed positive serum pregnancy test
- Noncompliance with trial treatment or procedure requirements
- The subject is lost to follow-up
- Completed 24 months of uninterrupted treatment with pembrolizumab or 35 administrations of study medication, whichever is later.

Note: 24 months of study medication is calculated from the date of first dose. Subjects who stop pembrolizumab after 24 months may be eligible for up to one year of additional study treatment if they progress after stopping study treatment provided they meet the requirements detailed in Section 7.1.5.5

- Administrative reasons

The End of Treatment and Follow-up visit procedures are listed in Section 6 (Protocol Flow Chart) and Section 7.1.5 (Visit Requirements). After the end of treatment, each subject will be followed for 30 days for adverse event monitoring (serious adverse events will be collected for 30 days after the end of treatment as described in Section 7.2.3.1). Subjects who discontinue for reasons other than progressive disease will have post-treatment follow-up for disease status until disease progression, initiating a non-study cancer treatment, withdrawing consent or becoming lost to follow-up. After documented disease progression each subject will be followed by telephone for overall survival until death, withdrawal of consent, or the end of the study, whichever occurs first.

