6.0 TRIAL FLOW CHART

6.1 Study Flow Chart

Trial Period:	Screening	Pembro Only	Doxorubicin/Pembrolizumab Combination							Pembrolizumab Only (repeat)				End of Treatment	
Treatment Cycle/Title:	Screening	1	2	3	4	5	6	7	8	9	10	11	At time of Discon	30 days post discon	
Scheduling Window (Days):	see section 7.1.5	± 3	± 3	± 3	± 3	± 3	± 3	± 3	± 3	± 3	± 3	± 3	± 7	± 7	

Trial Period:	Screening	Pembro Only	Doxorubicin/Pembrolizumab Combination							Pembrolizumab Only (repeat)				End of Treatment	
Treatment Cycle/Title:	Screening	1	2	3	4	5	6	7	8	9	10	11	At time of Discon	30 days post discon	
Scheduling Window (Days):	see section 7.1.5	± 3	± 3	± 3	± 3	± 3	± 3	± 3	± 3	± 3	± 3	± 3	± 7	± 7	
Informed Consent	X														
Inclusion/Exclusion Criteria	X														
Demographics and Medical History	X														
Prior and Concomitant Medication Review	X														
Trial Treatment															

Trial Period:	Screening	Pembro Only	Doxorubicin/Pembrolizumab Combination							Pembrolizumab Only (repeat)				End of Treatment	
Treatment Cycle/Title:	Screening	1	2	3	4	5	6	7	8	9	10	11	At time of Discon	30 days post discon	
Scheduling Window (Days):	see section 7.1.5	± 3	± 3	± 3	± 3	± 3	± 3	± 3	± 3	± 3	± 3	± 3	± 7	± 7	
Administration															
Post-study anticancer therapy status													X	X	
Survival Status													X	X	
Review Adverse Events		X	X	X	X	X	X	X	X	X	X	X	X	X	
Full Physical Examination	X														
Directed Physical Examination		X	X	X	X	X	X	X	X	X	X	X	X	X	
Vital Signs and	X	X	X		X			X	X		X	X	X	X	

Trial Period:	Screening	Pembro Only	Doxorubicin/Pembrolizumab Combination							Pembrolizumab Only (repeat)				End of Treatment	
Treatment Cycle/Title:	Screening	1	2	3	4	5	6	7	8	9	10	11	At time of Discon	30 days post discon	
Scheduling Window (Days):	see section 7.1.5	± 3	± 3	± 3	± 3	± 3	± 3	± 3	± 3	± 3	± 3	± 3	± 7	± 7	
Weight				X		X	X			X					
ECOG Performance Status	X	X	X	X	X	X	X	X	X	X	X	X	X	X	
EKG (Phase I portion)	X		X	X	X	X	X	X					X	X	
EKG (Phase II portion)	X		X			X							X	X	
Echo/MUGA (phase I)	X				X										
Echo/MUGA (phase II)	X														

Trial Period:	Screening	Pembro Only	Doxorubicin/Pembrolizumab Combination							Pembrolizumab Only (repeat)				End of Treatment	
Treatment Cycle/Title:	Screening	1	2	3	4	5	6	7	8	9	10	11	At time of Discon	30 days post discon	
Scheduling Window (Days):	see section 7.1.5	± 3	± 3	± 3	± 3	± 3	± 3	± 3	± 3	± 3	± 3	± 3	± 7	± 7	

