7.1.1.5.3 Subsequent Anti-Cancer Therapy Status

The investigator or qualified designee will review all new anti-neoplastic therapy initiated after the last dose of trial treatment. If a subject initiates a new anti-cancer therapy within 30 days after the last dose of trial treatment, the 30-day Safety Follow-up visit must occur before

the first dose of the new therapy. Once new anti-cancer therapy has been initiated the subject will move into survival follow-up.

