7.1.5.3.1 Safety Follow-Up Visit

The mandatory Safety Follow-Up Visit should be conducted approximately 30 days after the last dose of trial treatment or before the initiation of a new anti-cancer treatment, whichever comes first. All AEs that occur prior to the Safety Follow-Up Visit should be recorded. Subjects with an AE of Grade > 1 will be followed until the resolution of the AE to Grade 0-1 or until the beginning of a new anti-neoplastic therapy, whichever occurs first. SAEs that occur within 30 days of the end of treatment or before initiation of a new anti-cancer treatment, whichever is earlier, should also be followed and recorded. Subjects who are eligible for retreatment with pembrolizumab (as described in Section 7.1.5.5) may have up to two safety follow-up visits, one after the Treatment Period and one after the Second Course Phase.

If a patient goes onto hospice, then they will no longer be followed and considered withdrawn from the study.

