7.1.5.3.1 Survival Follow-up

Once a subject experiences confirmed disease progression or starts a new anti-cancer therapy, the subject moves into the survival follow-up phase and should be contacted by telephone every 12 weeks to assess for survival status until death, withdrawal of consent, or the end of the study, whichever occurs first.

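### Hospice entry ends all follow-up in three places while the survival follow-up rules run to death; if those patients are censored, OS reads too high, and PFS does too where hospice precedes recorded progression

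*Combined protocol and SAP*

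**What the plan says.** Hospice entry ends follow-up in three places. Section 5.6 states "A subject will be considered withdrawn and no longer followed if they enroll onto hospice care". Section 7.1.4.1 (Withdrawal/Discontinuation) repeats the sentence. Section 7.1.5.3.1 (Safety Follow-Up Visit) says "If a patient goes onto hospice, then they will no longer be followed and considered withdrawn from the study".

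Two passages on survival follow-up say otherwise:

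- Later in Section 5.6: "After documented disease progression each subject will be followed by telephone for overall survival until death". The only other exits are withdrawal of consent and study end.
- The Survival Follow-up subsection, which is also numbered 7.1.5.3.1: "Once a subject experiences confirmed disease progression or starts a new anti-cancer therapy, the subject moves into the survival follow-up phase", and such patients "should be contacted by telephone every 12 weeks to assess for survival status until death, withdrawal of consent, or the end of the study". Section 7.1.1.5.3 adds "Once new anti-cancer therapy has been initiated the subject will move into survival follow-up".

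Disease-status follow-up is also in 5.6: "Subjects who discontinue for reasons other than progressive disease will have post-treatment follow-up for disease status until disease progression". Its other exits are a non-study cancer treatment, withdrawn consent and loss to follow-up. Hospice is not among them.

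Section 3.2 lists PFS and OS as secondary endpoints. Section 8.2 names Kaplan-Meier for both medians and gives a precision of 14% with 51 patients for single-time-point estimates. It defines neither endpoint and says nothing about censoring.

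**The concern.** The two sets of instructions cannot both be followed for a patient who enters hospice. Being treated as withdrawn by the protocol is not the same as the patient withdrawing consent, so the exits listed for survival follow-up do not cover the case.

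If the hospice rule is applied, the natural handling is to censor at hospice entry or last contact, although the plan does not say so. Kaplan-Meier requires that a censored patient has the same outlook as those still at risk. A patient entering hospice is expected to die soon, so censoring there removes deaths and leaves a healthier risk set. OS is then biased upward.

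The same rule stops disease-status follow-up. A patient who enters hospice before progression is recorded is informatively censored for PFS too, whether or not death counts as a PFS event. Hospice entry after recorded progression does not change PFS.

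The control is historical (Section 1.1), so no concurrent arm would share the bias. Deaths not recorded during follow-up may be hard to recover at analysis.

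**Working it through.** **The plan's own figure.** The 95% half-width at a proportion of 50% is 1.96 × sqrt(0.25/n). At n = 51 this is 13.7 points, which rounds to the stated 14%. At the phase II n = 35 it is 16.6 points. The figure reproduces; here it serves only as a yardstick.

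**Inputs from the documents.** Median OS is about 12 months and median PFS about 4.6 months (Section 4.2.1). Accrual takes 24 months and the trial 48 months (Section 1.1), so administrative censoring falls between 24 and 48 months. Survival calls are every 12 weeks.

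**Assumptions.** The documents give neither the share h of deaths preceded by hospice nor the time from entry to death. I take h from 10 to 60%, an exponential lead with mean 1 or 2 months, and exponential survival. The medians below are Kaplan-Meier medians from large simulated samples (400,000 or more patients per setting).

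**Case 1: hospice is learned only at a 12-weekly call.** The patient is censored at the first call that falls between entry and death; if none does, the death is recorded. About a third of hospice patients are lost with a 1-month lead and about half with a 2-month lead.

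| h | median OS, 1-month lead | median OS, 2-month lead |
|---|---|---|
| 10% | 12.4 | 12.6 |
| 25% | 13.0 | 13.5 |
| 40% | 13.7 | 14.7 |
| 50% | 14.1 | 15.6 |
| 60% | 14.7 | 16.8 |

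12-month OS reads 51 to 57% with a 1-month lead, and up to about 60% with 2 months, against a true 50%.

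**Case 2, upper bound: every entry is known at once and censored.** The event hazard falls to about (1 − h) of its true value, so the median is about 12/(1 − h): 13.3, 16, 20, 24 and 30 months for h = 10, 25, 40, 50 and 60%. Simulation with a 1-month lead gives 13.2, 15.8, 19.6, 23.4 and 29 months, and 12-month OS of 53, 59, 65, 70 and 75%. Only in this case does the 12-month bias exceed the half-width: from h of about 36% at n = 51 and about 43% at n = 35.

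**Sampling noise.** With no hospice censoring and N = 35, the median OS estimate has a 95% sampling range of about 7 to 19 months.

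**PFS.** With a true median of 4.6 months and a 1-month lead, if 5, 10 or 20% of PFS events are replaced by censoring at hospice entry before recorded progression, the median reads about 4.8, 5.0 or 5.6 months. These shares are also assumed.

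**Hospice entry counted as the OS event for all hospice patients.** For h = 10 to 60% the median reads 11.9 down to 11.4 months (1-month lead) or 11.8 down to 10.9 (2-month lead), slightly low.

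**The case against.** The hospice sentence is specific, appears three times, and stands in the same Section 5.6 as the general follow-up text. It can be read as a deliberate exception, so that there is no contradiction. That is a fair reading, but it is the one under which deaths are lost and OS is biased.

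The likely size is also modest. For patients who have progressed, contact is by telephone every 12 weeks, so Case 1 is nearer the documented process than Case 2. Its shift lies inside the sampling range at N = 35, and its 12-month bias is below both half-widths. The secondary aim is exploratory and no OS test is planned. All of this stands and holds the severity down. It does not remove the point: a confidence interval displays sampling noise, whereas this bias runs in one direction and would not be visible.

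Three stronger readings are tempting, and the documents do not support them:

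- **A median OS of 23 to 29 months should be expected.** That needs immediate knowledge of every entry and a hospice share of 50 to 60%, neither of which is documented.
- **PFS is inflated for all hospice patients.** It is not affected once progression has been recorded.
- **A known share of deaths is lost even if the telephone rules govern.** Calls start only at progression or new therapy, so a patient entering hospice with neither has no scheduled survival call. But disease-status follow-up in 5.6 continues for patients off treatment without progression, so the site could still learn of the death. No share of lost deaths can be derived.

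**Conclusion.** The concern holds in a limited form. The hospice rule and the survival follow-up rules need reconciling, and Section 8.2 does not say how such patients are analysed. If the hospice rule is followed and they are censored, Kaplan-Meier OS reads too high; PFS does so only for entry before recorded progression.

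The direction is secure because hospice entry signals nearby death. The size is not, since it rests entirely on assumed hospice shares and lead times. With a true median of 12 months, the nearer-to-practice case overstates it by roughly 0.4 to 2.7 months (1-month lead) and by up to 4.8 months (2-month lead). The upper bound is far larger.

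Only secondary endpoints are touched. A reader might infer that the trial's conclusion is at risk, but the response rate, the stage 1 rule of 2 responses in 20 and the final rule of 10 in 35 do not depend on this. It should be fixed, at the low end of that category.

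**What to change.** 1. **Reconcile the follow-up text.** In Sections 5.6, 7.1.4.1 and 7.1.5.3.1 (Safety Follow-Up Visit), state that hospice entry ends study visits and scans but not vital-status follow-up. Let the existing 12-weekly contact, or a record check as consent allows, also cover patients who enter hospice without recorded progression or new therapy. Extending calls to every off-treatment patient is not needed.
2. **Add to Section 8.2.** Deaths from any cause, including after hospice entry, are OS events. OS is censored only at withdrawal of consent, loss to follow-up or study end, at the date last known alive. PFS counts death from any cause, including after hospice entry, and hospice entry is not itself a reason for censoring.
3. **Handle missing vital status.** If it is unknown after hospice entry for some patients, report how many and add a sensitivity analysis that counts hospice entry as their OS event. This errs low where censoring errs high, so on average the two analyses lie either side of the true value.

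The cost is a few sentences of wording and some extra contacts or record checks. OS will look less favourable than under hospice censoring. For patients who enter hospice before recorded progression, the PFS event may be a death dated later than the true progression. The consent pages are not available here, so whether they already allow contact with family or hospice staff has to be checked.
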